CASE
COMPREHENSIVE
CANCER CENTER

A Cancer Center Designated by the
National Cancer Institute

STUDY NUMBER: CASE 6117

ClinicalTrials.gov NCT #: NCT03190083

Protocol Date: 2/15/2019

STUDY TITLE: Efficacy of Digital Breast Tomosynthesis (DBT) in Addition to Standard 2-Dimensional Mammography in Evaluating Extent of Disease in Newly Diagnosed Breast Cancer Patients

PRINCIPAL INVESTIGATOR: [name]

Cleveland Clinic
Imaging Institute
Breast Imaging, Department of Diagnostic Radiology
[name]
[name]

[REDACTED]
[REDACTED]

CO- INVESTIGATOR:

[name], Cleveland Clinic, Breast Imaging, Department of Diagnostic Radiology
[name] Cleveland Clinic, Breast Imaging, Department of Diagnostic Radiology,
[name]. Cleveland Clinic, Breast Imaging, Department of Diagnostic Radiology

STATISTICIAN:

[name]
Case Comprehensive Cancer Center
Cleveland Clinic
[name]
[name]

[REDACTED]
[REDACTED]

STUDY COORDINATOR:

[REDACTED]
[REDACTED]

SPONSOR: Case Comprehensive Cancer Center

SUPPORT/FUNDING: Taussig Cancer Center research grant

PROTOCOL SUMMARY

Protocol Number/Title	CASE 6117 Efficacy of digital breast tomosynthesis (DBT) in addition to standard 2- dimensional mammography in evaluating extent of disease in newly diagnosed breast cancer patients
Study Phase	N/A
Brief Background/Rationale	The proposed project aims at impacting a large set of population of women with newly diagnosed breast cancer. One in every eight women is diagnosed with breast cancer in their lifetime (10). The study aims at comparing the role of DBT in addition to standard 2-D mammograms in all new breast cancer patients to assess for improved detection of the extent of the cancer and additional imaging findings that can impact surgical planning and treatment. Given the significance of the study, this may change the standard of care and practice at our institution.
Primary Objective	The primary objective of the study is to measure the frequency with which DBT alters the surgical plan. Only positive findings, like an additional site of cancer or DCIS (findings requiring surgical intervention), will be taken into account when estimating the frequency of changes to surgical management.
Secondary Objective(s)	Secondary Endpoint(s)
Exploratory Objective(s)	
 1.To measure the frequency and nature of additional findings like atypical pathology (atypical ductal/lobular hyperplasia, papilloma, LCIS) found on DBT. 2.To identify variables on 2D (e.g. dense breasts, architectural distortions, non-calcified masses) that might predict which patients would benefit from DBT. 3.To measure the proportion of patients undergoing additional work-up following the DBT, and the subset of these patients with benign findings (i.e. False Positives).
Sample Size	Enrollment goal - 150 Age - 25-85 years , gender - female
Disease sites/Conditions	Breast Cancer
Interventions	3dimensional tomosynthesis mammogram

ABBREVIATIONS

CCCC	Case Comprehensive Cancer Center
CRF	Case Report Form
DCRU	Dahm's Clinical Research Unit
DSTC	Data Safety and Toxicity Committee
FDA	Food and Drug Administration
ICF	Informed Consent Form
IRB	Institutional Review Board
PRMC	Protocol Review and Monitoring Committee
SOC	Standard of Care
CCF	Cleveland Clinic Foundation
UH	University Hospitals

TABLE OF CONTENTS

1.0 Introduction

1.1 Background / Rationale

Currently, only MRI is occasionally used to evaluate the extent of disease in some cancer patients, based on age, breast density and pathology subtype of the breast cancer. It is a sensitive, but relatively expensive, time consuming test given the additional work up (second look ultrasounds and biopsies) required for findings noted on the MRI. This adds to both the diagnosis cost and time to treat. It also helps in assessing chemotherapy response and surgical treatment planning.

Our goal is to evaluate the efficacy of DBT in a similar fashion to study its role in cancer extent evaluation, finding additional ipsilateral and contralateral cancers, assess for multicentric and multifocal disease and study the role in post chemotherapy treatment planning. This is an easily accessible, readily available, time efficient, cost-friendly modality which may prove useful in providing additional information in all new breast cancer patients, since MRI is performed only in a select group of patients. This may prove specifically helpful in patients with non-calcified masses and architectural distortion. In a recent study on DBT, cancers that manifested as architectural distortion at diagnosis included a higher percentage of invasive lobular carcinomas (20%) (11). It may also lead to better mass margin assessment, tumor size and presence of satellite lesions. It is also a useful tool in evaluating the contralateral breast, especially since breast MRI is not performed in every new breast cancer patient at our institution.

2.0 Objectives

The primary aim of the study is to study the efficacy and additional role of digital breast tomosynthesis (DBT) for patients with a new diagnosis of breast cancer. In the current clinical practice at our institution, standard 2-dimensional (2-D) mammograms (DM) are performed as standard of care to evaluate the extent of disease in patients with new diagnosis of breast cancer. DBT (colloquially referred to as a 3-dimensional mammogram) is only occasionally performed, at the discretion of the breast radiologist to further evaluate the findings of the 2-D mammogram. Recently published data shows a greater efficacy of DBT with increased cancer detection and a reduced call back rate for screening mammography (1-4). Chudgar et al assessed MR extent of disease for cancers detected on DBT versus DM alone (5). Additional studies evaluated role of DBT in cancer detection and tumor size assessment in comparison to other diagnostic modalities (6-8), specifically Mariscotti et al assessed its role in characterizing invasive lobular cancers (9). Our hypothesis is that DBT may provide additional information to evaluate the extent of disease, including possible multifocality and multicentricity and additional findings including margin assessment and tumor size that would aid in staging a new breast cancer patient. This would impact surgical planning and improve patient outcomes. DBT is a relatively inexpensive test; in comparison to breast MRI which is the alternative study performed to evaluate extent of disease in selected new breast cancer patients. One of the reasons that a breast radiologist may recommend a breast MRI for a new breast cancer patient is if the patient has dense breast tissue on mammography. Performing DBT in these patients may improve the mammographic information about the extent of disease. Also, all the previously recently published studies were performed using different vendor versions of DBT other than Siemens used at our site.

2.1 Primary Objective

The primary objective of the study is to measure the frequency with which DBT alters the surgical plan to mastectomy versus lumpectomy. Only positive findings, like an additional site of cancer or DCIS (findings requiring surgical intervention), will be taken into account when estimating the frequency of changes to surgical management.

2.2 Secondary Objective(s)

Secondary Objectives include:

1. To measure the frequency and nature of additional findings like atypical pathology (Atypical ductal/ lobular hyperplasia, papilloma, LCIS found on DBT.)
2. To identify variables on 2D (e.g. dense breasts, architectural distortions, non-calcified masses) that might predict which patients would benefit from DBT.
3. To measure the proportion of patients undergoing additional work-up following the DBT, and the subset of these patients with benign findings (i.e. False Positives).

3.0 Study Design

A prospective cohort blinded study will be performed on new breast cancer patients detected at our Breast centers at Main campus and Beachwood family health center between May 2017 and August 2019. The patients assigned a BIRADS 5 category at the time of diagnosis and all new diagnosed breast cancer patients, will undergo a separate 2-D plus DBT in addition to the standard 2-D mammogram performed at our institution at Main campus and Beachwood Family health center. The new breast cancer patients will be scheduled for the mammogram after diagnosis at the time of surgical appointment. The radiologist reviewing the tomosynthesis images will be separate and blinded from the radiologist who reviewed the initial 2-D mammogram. The following pertinent data will be collected, including number of additional lesions, size of the lesion, margins of the lesions, percentage of biopsy rates, cancer detection rate, high risk lesion detection rate, lesions resulting in excisional biopsy, lesions changed to mastectomy, time to treat, false positive pathology. The principal investigator and key personnel will periodically review all the new patients on a weekly basis. The first 150 patients acquired during the study time period will be evaluated to assess for their imaging findings and compared to the initial standard diagnostic mammogram workup.

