14.0 STATISTICAL CONSIDERATIONS

The primary objective of the study is to measure the frequency with which DBT alters the surgical plan. For this objective, the proportion of subjects with a change in surgical plan will be calculated and its 95% Confidence Interval (CI) constructed. Logistic regression models will be used to identify variables on 2D that are predictive of patients who would benefit from DBT.

The dependent variable in the models will be change/no change in surgical plan, and the independent variables will be lesion and breast characteristics. Holm's method will be used to control the family-wise type I error rate. McNemar's test will be used to compare the findings on MRI and DBT.

Sample Size Justification:

A 95% CI for the proportion of patients with changes in their surgical plan attributable to DBT can be constructed with width of +/- 8% or tighter with 150 patients.

REFERENCES

3. Skaane P, Bandos AI, Gullien R, et al. Prospective trial comparing full-field digital mammography (FFDM) versus combined FFDM and tomosynthesis in a

population-based screening programme using independent double reading with arbitration. *Eur Radiol* 2013;23(8):2061–2071.

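### The reader and an added 2-D exam change together with DBT, so the primary proportion describes the package and cannot be credited to DBT alone

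*Combined protocol and SAP*

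**What the plan says.** Under section 3.0 (Study Design), patients "will undergo a separate 2-D plus DBT in addition to the standard 2-D mammogram performed at our institution". On reading, the same section states: "The radiologist reviewing the tomosynthesis images will be separate and blinded from the radiologist who reviewed the initial 2-D mammogram". The comparator is the initial workup: the first 150 patients are to be "evaluated to assess for their imaging findings and compared to the initial standard diagnostic mammogram workup".

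The Protocol Summary, section 2.1 and section 14.0 all frame the result as an effect of DBT: "The primary objective of the study is to measure the frequency with which DBT alters the surgical plan". Section 2.1 limits what counts: "Only positive findings, like an additional site of cancer or DCIS (findings requiring surgical intervention), will be taken into account". The sample size text in section 14.0 gives the target and precision of the 95% interval as follows: "changes in their surgical plan attributable to DBT can be constructed with width of +/- 8% or tighter with 150 patients". For the predictor analysis, "The dependent variable in the models will be change/no change in surgical plan".

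The plan does not describe a recorded read of the repeat 2-D alone by the second radiologist, a same-reader comparison, or a rule that the triggering finding must be visible only on DBT. The one paired test, McNemar's, compares MRI with DBT. Who reads the repeat 2-D is not stated, nor whether the second radiologist knows the diagnosis or sees the initial images.

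**The concern.** Two radiologists reading 2-D mammograms of the same patient will not always report the same lesions, and a repeat acquisition can show something that the first did not. Suppose the second radiologist finds a true additional cancer that was already visible on 2-D. It is counted as a plan change in the same way as a lesion visible only on DBT. Counting only positive findings removes false-positive changes, but does not show which component found the lesion.

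At stake is what the primary result means. The Protocol Summary says the study may change the institution's standard of care, and that decision turns on what DBT adds. The confidence interval covers sampling error only, so it gives no warning of a contribution from the reader or the repeat 2-D. The logistic model uses the same outcome. Its predictors would therefore describe who gains from the package, not who gains from DBT.

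**Working it through.** **1. The plan's own figure.** Inputs from section 14.0: 95% confidence, n = 150, half-width 8 points. The Wald half-width is 1.96 × sqrt(p(1−p)/n). At the worst case p = 0.5 it is 1.96 × sqrt(0.25/150) = 0.080, so the figure reproduces. At an observed 10% (15/150) it is 1.96 × sqrt(0.09/150) = 0.048. The precision is correct for the package proportion; the problem is what the proportion is said to measure.

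**2. What differs between the two sides of the comparison.**

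| | Initial workup | Study examination |
|---|---|---|
| Reader | First radiologist | Different, blinded radiologist (for the DBT images) |
| 2-D | Standard exam | A separate, later exam |
| DBT | Occasional, discretionary (section 2.0) | All patients |

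If the second radiologist does not read the repeat 2-D, the change of reader still remains.

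**3. How large the non-DBT part could be.** The documents give no inputs, so everything here is assumed. Let p be the share of patients with an additional focus visible on 2-D (10–30%), s the sensitivity of one 2-D read (0.4–0.8), r the correlation between reads (0–0.5), and f the share of new finds that change the plan (25–75%). With no DBT benefit, plan changes = p × s(1−s) × (1−r) × f.

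- Minimum: 0.1 × 0.16 × 0.5 × 0.25 = 0.2% (0.3 of 150).
- Maximum: 0.3 × 0.25 × 1 × 0.75 = 5.6% (8.4 of 150).
- Mid case, r = 0: 0.2 × 0.24 × 1 × 0.5 = 2.4% (3.6 of 150).
- Mid case, r = 0.5: 1.2% (1.8 of 150).

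If 15 of 150 plans changed, the mid cases would be 3.6/15 = 24% and 1.8/15 = 12% of the changes.

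**4. Direction.** Let S1 be the first reader's 2-D sensitivity, D1 the same reader's with DBT, and D2 the second reader's with 2-D plus DBT. The package count per focus is (1−S1)D2 − r × sqrt(S1(1−S1)D2(1−D2)); the same-reader gain is D1 − S1. Assume S1 = 0.8 and D1 = 0.9, a gain of 10 per 100 foci.

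| D2 | r = 0 | r = 0.5 |
|---|---|---|
| 0.9 | 18 | 12.0 |
| 0.7 | 14 | 4.8 |

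The package can lie above or below the gain.

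**5. Would counting only DBT-step finds give the DBT effect?** Suppose the second reader reads 2-D first and then DBT. Assume equally sensitive readers (2-D sensitivity s, with DBT D), the same r for both pairs of reads, and no 2-D find lost at the DBT step. The DBT-step count is the package minus the 2-D step, where the 2-D step is s(1−s)(1−r). Per 100 foci:

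| s, D, r | Same-reader gain | Package | 2-D step | DBT step |
|---|---|---|---|---|
| 0.6, 0.8, 0 | 20 | 32 | 24 | 8 |
| 0.6, 0.8, 0.5 | 20 | 22.2 | 12 | 10.2 |
| 0.8, 0.9, 0.5 | 10 | 12 | 8 | 4 |

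The DBT-step count measures what DBT adds beyond two 2-D reads. In these cases it misses the same-reader gain by as much as the package does (first row) or by more (the other two).

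**6. Patients still to be read.** The window in section 3.0, taken as 1 May 2017 to 31 August 2019, is 852 days. The protocol date of 15 February 2019 is day 655, or 77%. Under uniform accrual (assumed; accrual is not reported), 150 × 0.769 = 115 patients have been read and about 35 remain. The half-width at an observed 10% is then 1.96 × sqrt(0.09/35) = 9.9 points.

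**The case against.** The design has a rationale. A separate blinded reader avoids anchoring on the first read, section 3.0 states the comparison openly, and the study title presents DBT as an addition to 2-D. The yield of an add-on examination is a legitimate pragmatic quantity. All of this stands, and it supports the package estimate. It does not support crediting the result to DBT.

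Materiality is also unproven. Every input in step 3 is assumed, and the mid case at correlation 0.5 (1.2 points) lies well inside the 4.8-point sampling half-width at 10%. The comparator may be more than one 2-D read: section 1.1 describes MRI in some patients, and section 2.0 says DBT "is only occasionally performed, at the discretion of the breast radiologist to further evaluate the findings of the 2-D mammogram". Lesions missed on the first 2-D read may already be in the surgical plan by those routes, which would lower the yield in step 3. This stands: the non-DBT part could be near zero.

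A reader might infer that the proportion must overstate the effect of DBT. The documents do not establish that. Disagreement between equally sensitive readers raises the count, since only positive findings are counted; a less sensitive second reader, or DBT already used in the initial workup, lowers it. The reader-based understatement in step 4 is the more strained case. The package count cannot fall below D2 − S1, so it drops below the gain only if the second reader with DBT is less sensitive than the first reader would be with it.

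A reader might also infer that a DBT-step count should become the primary endpoint. Step 5 shows why not: it can be further from the same-reader gain than the package is, and few patients may remain unread.

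**Conclusion.** The attribution is not supported as written. The primary proportion is valid for the second reader, repeat 2-D and DBT taken together. The plan provides nothing that would let sections 2.1 and 14.0, or the Protocol Summary, assign it to DBT alone, and the logistic analysis has the same limit. This conclusion rests on the text of section 3.0 and on none of the assumed values.

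The size and net direction of the non-DBT part cannot be derived from the documents. The range of 0.2% to 5.6% of patients is illustrative only. It would be wrong to read this as an error in the sample size or as invalid data: the 8-point half-width reproduces and all 150 patients remain usable. That the second radiologist also reads the repeat 2-D is an inference, but the conclusion does not depend on it.

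**What to change.** 1. **Name the estimand.** Keep the primary proportion in all 150 patients. In sections 2.1 and 14.0, and in the Protocol Summary's copy of the objective, describe it as the yield of a second-reader 2-D plus DBT examination over the initial workup. Remove the attribution to DBT from the sample size sentence, and word the logistic analysis the same way. This costs only wording and keeps the 8-point precision, but gives up the DBT-specific claim.

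2. **Add a supporting same-reader record.** For patients not yet read, have the second radiologist record and lock findings on the repeat 2-D before opening DBT. Report how many pathology-confirmed additional lesions, and how many resulting plan changes, that reader first saw at each step. No extra reader or exam is needed, because the separate 2-D is already in the design. State in section 3.0 who reads the repeat 2-D and what that reader knows and sees.

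3. **Do not make the DBT-step count the primary endpoint**, for the reason in step 5 of the working.

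Costs of item 2: a few minutes of reading per case (assumed); possible under-calling at the 2-D step by a reader who knows DBT follows, which would favour DBT; and low precision if few patients remain (9.9 points at an observed 10% with about 35 unread).

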3.2 Number of Subjects

Approximately 150 subjects will be enrolled in this trial.

4.0 Inclusion Criteria

Subjects must meet all of the following inclusion criteria to be eligible for enrollment:

1. New diagnosis of breast cancer
2. New diagnosis if a previous breast cancer patient with negative surgical margins
3. Age limit: 25-85 years

Exclusion Criteria

The presence of any of the following will exclude a subject from study enrollment.

1. Male patients
2. High risk benign lesions as the primary pathology diagnosis
3. Patients under 25, over 85

4.1 Inclusion of Women and Minorities

Women and members of all races and ethnic groups are eligible for this trial.

5.0 REGISTRATION

All subjects who have been consented are to be registered in the OnCore™ Database. For those subjects who are consented, but not enrolled, the reason for exclusion must be recorded.

All subjects will be registered through the Cleveland Clinic and will be provided a study number by contacting [the study coordinator listed on the cover page](#).

Institutional Review Board Reporting Requirements:

- Investigative sites will report adverse events to their respective IRB according to the local IRB's policies and procedures in reporting adverse events.

SAEs and OnCore

- All SAEs will be entered into OnCore.
- A copy of the SAE form(s) submitted to the sponsor-investigator is also uploaded into Oncore.

6.0 DATA SAFETY AND TOXICITY COMMITTEE

It is the responsibility of each site PI to ensure that ALL SAEs occurring on this trial (internal or external) are reported to the Case Comprehensive Cancer Center's Data and Safety Toxicity Committee. This submission is simultaneous with their submission to the sponsor and/or other regulatory bodies

The sponsor-investigator is responsible for submitting an annual report to the DSTC as per CCCC Data and Safety Monitoring Plan.

7.0 DATA SAFETY AND MONITORING PLAN

This protocol will adhere to the policies of the Case Comprehensive Cancer Center Data and Safety Monitoring Plan in accordance with NCI guidelines.

8.0 DATA REPORTING / REGULATORY CONSIDERATIONS

Adverse event lists, guidelines, and instructions for AE reporting can be found in Section [8.0](#) (Adverse Events: List and Reporting Requirements).

8.1 Data Reporting

The OnCore™ Database will be utilized, as required by the Case Comprehensive Cancer Center, to provide data collection for both accrual entry and trial data management. OnCore™ is a Clinical Trials Management System housed on secure servers maintained at Case Western Reserve University. OnCore™. Access to data through OnCore™ is restricted by user accounts and assigned roles. Once logged into the OnCore™ system with a user ID and password, OnCore™ defines roles for each user which limits access to appropriate data. User information and password can be obtained by contacting the OnCore™ Administrator at [contact].

OnCore™ is designed with the capability for study setup, activation, tracking, reporting, data monitoring and review, and eligibility verification. This study will utilize electronic Case Report Form completion in the OnCore™ database. A calendar of events and required forms are available in OnCore™.

9.0 REGULATORY CONSIDERATIONS

The study will be conducted in compliance with ICH guidelines and with all applicable federal (including 21 CFR parts 56 & 50), state or local laws.

10.0 WRITTEN INFORMED CONSENT

The Principal Investigator will ensure that the subject is given full and adequate oral and written information about the nature, purpose, possible risks and benefits of the study as well as the subject's financial responsibility. Subjects must also be notified that they are free to discontinue from the study at any time. The subject should be given the opportunity to ask questions and be allowed time to consider the information provided.

The original, signed written Informed Consent Form must be kept with the Research Chart in conformance with the institution's standard operating procedures. A copy of the signed written Informed Consent Form must be given to the subject. Additionally, documentation of the consenting process should be located in the research chart.

